6.2.1 Definition of Adverse Event (AE)

AE means any untoward medical occurrence associated with the use of an intervention in humans, whether or not considered intervention-related (21 CFR 312.32 (a)). An AE can therefore be any unfavorable and unintended sign (including an abnormal clinical laboratory finding), symptom or disease temporally associated with the use of medicinal (investigational) product.

Any medical condition that is present at the time that the subject is screened will be considered as baseline and not reported as an AE. However, if the severity of any pre-existing medical condition increases, it should be recorded as an AE.

AEs can be further divided into solicited AEs and unsolicited AEs. Solicited AEs are those for which the study team will specifically query the subject whether they occurred. Unsolicited AEs are those events that the subject report occurring without being queried about the specific event.

All AEs will be assessed for severity and relationship to study intervention. Reporting of all AEs, solicited and unsolicited, will occur during the period from study device administration on Day 1 through Day 14 or until an early termination visit.

All AEs, solicited and unsolicited, will be captured on the appropriate e-CRFs. Information to be collected for AEs includes event description, date of onset, assessment of severity, relationship to study product and alternate etiology (assessed only by those with the training and authority to make a diagnosis as the participating clinical site PI or appropriate sub-investigator), date of resolution, seriousness, and outcome. AEs occurring during the study-collection and reporting period will be documented appropriately regardless of relationship.

AEs will be followed to resolution or stabilization.

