| Physical Examination | X | *Targeted only | *Targeted only | *Targeted only |
| BMI | X | | | |
| Vital Signs | X | X | X | X |
| Methemoglobin | X | *Before and 60 minutes after device use | *Before and 60 minutes after device use | *Before and 60 minutes after device use |
| Lab Sample Collection & Processing | X | | | X |
| CBC and differential | X | | | X |
| CMP | X | | | X |
| Urinalysis | X | | | X |
| Urine Pregnancy Test | X | | | X |
| Concomitant Medication History/New | X | X | X | X |
| Device Illumination | | X | X | X |
| Acceptability Assessment of Device | | X | X | X |
| Distribution and train diary card | | X | | |

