3.2 Objectives and Outcomes

| OBJECTIVES | ENDPOINTS (OUTCOME MEASURES) |
|------------|--|
| Primary | 
Evaluation of the acute safety of the EmitBio™ RD19 device. 
Frequency, grade and attribution of each incident local and systemic AE during the 14 day study period.Frequency and attribution of any incident SAEs during the 14 day study period. |
| Secondary | 
Evaluation of the acceptability of the EmitBio™ RD19 device. 
Ease of use, clarity of user instructions, & compliance with per protocol schedule and, if out of compliance, reason(s) for noncompliance. |

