5.5 Device Discontinuation

5.5.1 Study Pausing Criteria

RD19-01-3Q20 will be paused if any of the following events occur:

- Any subject experiences an SAE after use of the RD19 Device that is considered related to RD19.
- Any subject experiences laryngospasm, bronchospasm or anaphylaxis within 2 hours after use of the RD19 Device that is considered related to RD19.
- Two (2) or more subjects experience an allergic reaction such as generalized urticaria (defined as occurring at three or more body parts) within 72 hours after administration of light that is considered related to RD19.
- Three (3) or more subjects experience a \geq Grade 3 AE (systemic and/or clinical laboratory abnormality), in the same SOC grouping of Preferred Terms based on the Medical Dictionary for Regulatory Activities (MedDRA) coding, considered to be related to RD19.

Study device use and enrollments may resume only after review of the AEs that caused the pause results.

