 - Reactogenicity assessments will include an assessment of illumination site reactions – erythema, edema/induration, pain and difficulty swallowing, as well as systemic reactions—fever, chills, headache, and nausea. Pre-illumination reactogenicity assessments will be performed immediately prior to first RD19 use to establish a baseline, then the use of the RD19 device will occur.
- Subjects will be observed in the clinic for at least 60 minutes post each RD19 illumination. The illumination site will be examined, post-use reactogenicity assessments will be performed, and any AEs/SAEs will be recorded on the appropriate e-CRF prior to discharge from the clinic. The oropharynx and surrounding tissues will also be examined on Days 1, 7, 14 and during unscheduled visits and early termination visits.
- Vital signs:
- Vital sign measurements will include systolic and diastolic BP, HR, and oral temperature. Vital signs will be measured at timepoints specified in the SOA. On Days 1, 7 and 14, vital sign measurements will be collected prior to device administration. Vital signs assessed on Day 1 prior to the first use of RD19 will be considered as baseline. Subjects must not eat or drink anything hot or cold within 10 minutes prior to taking their oral temperature or using the RD19 device.
- Clinical laboratory evaluations:
 - Fasting is not required before collection of clinical laboratory evaluations.
 - Urine pregnancy test will be performed locally by the site laboratory at the screening visit and at the final study visit. Results must be confirmed as negative prior to randomization on Day 1 and allocation and use of the RD19 device.
 - Clinical screening laboratory evaluations (CMP and CBC (diff) will be performed locally by the site laboratory).
 - Clinical safety laboratory evaluations will be performed locally by the site laboratory.
 - Methemoglobin will be measured prior to use of the device in the clinic and just prior to discharge from the clinic after 1 hour.
 - Blood and urine will be collected at timepoints specified in the SOA.

○ Diary Cards:

- All subjects will complete a Diary Card daily for the entire term of the study. Diary Cards will be reviewed with the subjects for any AEs (solicited injection site and systemic reactions, as well as unsolicited AEs), SAEs and concomitant medications. Diary Cards will be collected at the end of a volunteer's participation in the study.

○ Acceptability Assessment:

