7.4 Statistical Analyses

7.4.1 Primary Safety Analyses

Summaries and analyses of safety data will be presented for the Safety Analysis Population.

Solicited AEs will be summarized overall and by maximum severity post through study day 7, post study period days 7 -14 and overall. Additionally, solicited AEs will be analyzed by taking the most severe response (grouped as either modified per protocol or per protocol), dichotomizing into a binary variable (none versus mild, moderate, or severe) and using standard techniques, such as exact confidence intervals (CI), to summarize the proportion of subjects reporting each solicited sign or symptom.

Unsolicited non-serious AEs will be collected from the time of first device use through study day 14. Unsolicited AEs will be coded by MedDRA™ for preferred term and system organ class (SOC). All SAEs will be collected from the time of first device use through the study day 14. The number of SAEs will be reported by detailed listings showing the event description, MedDRA™ preferred term and SOC, study day of occurrence, severity, relatedness, and outcome for each event. Non-serious unsolicited AEs will be summarized as number and percentage of subjects reporting at least one event in each MedDRA□ preferred term and SOC, cross tabulated by severity and relationship to the study device. Additionally, the proportion of subjects and exact 95% CIs of AEs in aggregate and by MedDRA□ categories will be computed.

Clinical laboratory data, including methemoglobin measurements, will be summarized by severity and as the maximum numeric value over the entire study. Graphical presentations may include box plots and shift plots.

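### Collection of new adverse events ends on Day 14, the day of the last scheduled device use, although one pausing criterion looks 72 hours beyond a use

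*Combined protocol and SAP*

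**What the plan says.** - **AE window.** Section 6.2.1 states that reporting of all AEs "will occur during the period from study device administration on Day 1 through Day 14 or until an early termination visit". Section 7.4.1 repeats the limit for analysis: "Unsolicited non-serious AEs will be collected from the time of first device use through study day 14", and "All SAEs will be collected from the time of first device use through the study day 14". Section 6.2.3 ends unsolicited reporting at study termination.
- **Endpoint.** The primary endpoint in Section 3.2 (and Table 1) is the frequency, grade and attribution of each "incident local and systemic AE during the 14 day study period".
- **Use on the last day.** Table 3 in Section 1.2 marks "Device Illumination" at Day 1, Day 7 and the final Day 14/early termination column. Section 6.2 agrees: "On Days 1, 7 and 14, vital sign measurements will be collected prior to device administration".
- **After that use.** Section 6.2 requires at least 60 minutes of observation and places the last methemoglobin reading just before discharge at 1 hour. Diary cards are handed in when participation ends, and under Section 5.5.2 so is the device. Table 3 has no later column.
- **The 72-hour window.** Section 5.5.1 pauses the study if two or more subjects have an allergic reaction such as generalized urticaria "within 72 hours after administration of light that is considered related to RD19".
- **After Day 14.** Sections 6.2.1 and 6.2.2 follow events already begun until they resolve or stabilise. Section 6.2.6 has the site report a suspected related SAE if it learns of one after the study.

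**The concern.** The pausing criteria accept that an allergic reaction can appear up to three days after light and still count towards halting the study. The data collection plan does not look that far after the last uses. A subject who uses the device at the Day 14 visit, leaves an hour later and develops mild or moderate urticaria or oral erythema the next day is asked nothing further.

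This is a first-in-man study whose primary purpose is safety, so completeness of ascertainment after the final uses matters in itself. There is also a practical consequence. Subjects enter over about a week (Section 4), so the first to finish do so while others are still using the device. A late reaction in an early finisher could be one of the two needed for the allergic-reaction pause.

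**Working it through.** The plan states no figure on this point, so there is none to reproduce. The check is a timeline.

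**Inputs from the protocol:** two uses a day, at least 4 and ideally 8 to 12 hours apart (Section 1.1); one clinic use on Day 14 (Table 3); discharge after about 1 hour (Section 6.2); 72 hours (Section 5.5.1); enrolment over one week (Section 4).

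**Assumptions, not in the protocol:** home use at 08:00 and 20:00; Day 14 clinic use at 09:00; discharge at 10:00.

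**Step 1, number of uses.** 13 days × 2 + 1 = 27 per subject.

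**Step 2, rule.** A use at time u has follow-up C − u, where C is the close of collection. Its window is cut short if C − u < 72 hours.

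**Step 3, close at discharge.** C is 10:00 on Day 14, so the 72-hour cut falls at 10:00 on Day 11. The later uses are:

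| Use | Follow-up (h) |
|---|---|
| Day 11, 20:00 | 62 |
| Day 12, 08:00 | 50 |
| Day 12, 20:00 | 38 |
| Day 13, 08:00 | 26 |
| Day 13, 20:00 | 14 |
| Day 14, 09:00 | 1 |

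That is 6/27 = 22%, and the last use has 1/72 = 1.4% of the window. With the morning use moved to 09:00 and daily gaps of 4, 8 or 12 hours, the count is again 6 of 27.

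**Step 4, close at the end of Day 14.** If the window is read as the whole calendar day, the cut moves to midnight at the end of Day 11. The uses left are two on Day 12, two on Day 13 and one on Day 14: 5/27 = 19%. The last use then has 15 hours (15/72 = 21%). A second use on Day 14 would make it 6/28 = 21%. No contact is scheduled to gather information from those extra hours.

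**Step 5, overlap with the pausing rule.** Suppose a subject starts k days before the last one enrolled. That subject's 72 hours end on own Day 17, and the last subject finishes on the first subject's Day 14 + k. Since 17 ≤ 14 + k when k ≥ 3, anyone starting at least 3 days before the last subject has the whole 72 hours inside someone else's period of device use.

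**Step 6, after the fix.** If C is 72 hours after the last use (about Day 17), 0 of 27 uses are cut short.

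**The case against.** The strongest reply is that the endpoint is defined as AEs in the 14-day period and the objective in Section 3.2 is acute safety. An event starting on Day 15 lies outside that endpoint by design. This stands. A reader might infer that the primary AE frequency is biased downward, but the stated quantity remains estimable. What is incomplete is ascertainment after the last uses.

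Three other stronger readings are tempting, and the protocol does not support them:

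- **That 72 hours is the protocol's general window for device reactions.** It belongs to one criterion, for allergic reactions, which also needs a judgement of relatedness. The criterion for laryngospasm, bronchospasm and anaphylaxis uses 2 hours, and the SAE and Grade 3 criteria have no window.
- **That a reaction after Day 14 could not count towards a pause.** Section 5.5.1 has no Day 14 cut-off, so an event the site heard about could be weighed. The weakness is that nothing is planned to make the site hear of it. Section 3.1 asks volunteers to call about urgent events or those worse than moderate, which leaves out the milder ones.
- **That the last uses are the most hazardous because exposure has accumulated.** The protocol offers no evidence of cumulative toxicity. Section 2.2.1 ties erythema and thermal injury to exceeding the directed time.

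It is also fair to say that the 6 of 27 counts uses, whereas Section 7.4.1 summarises subjects with at least one event. Four of the six shortened uses still have more than 24 hours. For early terminators the time from last use to the visit is not specified, and Section 5.5.3 asks for safety follow-up where possible, so how far they are cut short is unknown.

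**Conclusion.** The concern holds as a gap in active follow-up. The device is used at the last visit, new AEs are collected only through that day, and one pausing criterion reaches 72 hours beyond a use. New non-serious reactions after the final uses have no planned capture, and related SAEs are covered only if the site becomes aware of them.

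The gap touches 6 of 27 uses per completer, or 5 of 27 if collection runs to midnight. Both counts rest on assumed clock times, although the count of 6 does not change for daily gaps of 4, 8 or 12 hours. The effect on the 14-day AE proportions is probably small, because at least 21 of 27 uses have the full 72 hours. One newly affected subject would move a proportion by 1/25 = 4 percentage points, but the protocol gives no basis for saying how many would be missed. The more practical consequence is a late reaction in an early finisher passing unseen while the pausing rule still applies to others. This is an inexpensive improvement. It does not invalidate the declared analysis.

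**What to change.** 1. Add one telephone contact by existing site staff at least 72 hours after each subject's last device use, including after early termination. Use the solicited list in Section 6.2.2 and an open AE question, and let the subject keep the diary until then.
2. Extend the AE and SAE windows in Sections 6.2.1, 6.2.3 and 7.4.1 to that contact, add it to Table 3, and align the endpoint wording in Table 1 and Section 3.2.
3. Report events with onset after Day 14 separately, so that the 14-day summary is kept as planned.
4. Update the subject and study durations in Section 1.1.4. Both are given as at most 18 days, but screening up to 7 days ahead plus 14 study days is already about 21 days at its longest. Three more days make about 24.

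**Cost.** One short call and about 3 more days of follow-up per subject, plus an IRB-approved amendment with any matching consent and e-CRF changes. A call cannot examine the mouth, so visible signs such as erythema or edema would rest on the subject's report unless an unscheduled visit follows.

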6.2.2 Solicited Adverse Events

Solicited AEs are anticipated local and systemic AEs for which consistent collection of information is desired. Study clinicians will follow and collect resolution information for any reactogenicity symptoms that are not resolved during the active study period.

Solicited AEs (i.e., reactogenicity) will be collected using a diary card and recorded on the appropriate e-CRF from the during the entire course of the study.

For this study, solicited AEs include:

- Illumination site Pain
- Illumination site Erythema
- Illumination site Edema/Induration
- Headache
- Difficulty swallowing
- Nausea
- Fever
- Chills

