2.2 Risk/Benefit Assessment

2.2.1 Known Potential Risks

The potential risks of participating in this trial are those associated with having blood drawn and unlikely, but possible, mild local reactions to the EmitBio™ RD19, entirely unknown adverse events, and inadvertent breach of confidentiality.

Drawing blood may cause transient discomfort and fainting. Fainting is usually transient and managed by having the subject lie down and elevate his/her legs. Bruising at the blood draw site may occur but can be prevented or lessened by applying pressure to the blood draw site for a few minutes after the blood is taken.

Extensive evaluation of the RD19 and similar energy-based devices routinely used for oral and skin care purposes have resulted in the Sponsor, after careful consideration, making the determination that RD19 as a “Not Significant Risk” (NSR) device per FDA guidelines.

EmitBio™ RD19 is expected to be without significant risk for acute adverse events when used as directed. If the RD19 device is not used as directed, for example is inserted into the oral cavity improperly it is possible the user could induce a gag reflex. If the RD19 device is used for a period of time in excess of the time directed, it is possible the user could experience mild to moderate erythema, and under extreme overuse conditions the user could experience oral mucosal thermal injury, especially to the uvula.

Eye exposure is to be avoided. Direct illumination of unprotected eyes can result in damage to the retina, and especially the macula. Other eye structures can also experience thermal injury. Study staff must ensure volunteers understand to never point the RD19 device toward their or anyone else's eyes.

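### Eye injury and gagging are named device risks, but neither is a solicited AE, so a zero count for them would be weaker evidence than Section 7.2 assumes

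*Combined protocol and SAP*

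**What the plan says.** Section 6.2.1 separates solicited from unsolicited events by whether a specific question is asked: "Solicited AEs are those for which the study team will specifically query the subject whether they occurred". Section 6.2.2 gives the purpose of the list: "Solicited AEs are anticipated local and systemic AEs for which consistent collection of information is desired". It then names eight terms: illumination site pain, erythema and edema/induration, headache, difficulty swallowing, nausea, fever and chills.

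Section 2.2.1 sets out the device risks. On the eyes: "Direct illumination of unprotected eyes can result in damage to the retina, and especially the macula". It adds that other eye structures can suffer thermal injury. On insertion, the misuse case is put this way: "for example is inserted into the oral cavity improperly it is possible the user could induce a gag reflex". On use beyond the directed time: "it is possible the user could experience mild to moderate erythema, and under extreme overuse conditions the user could experience oral mucosal thermal injury". It also allows for mild local reactions.

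Section 6.2 provides a full physical examination at screening, including the eyes. Later examinations are symptom-directed and done if indicated. After clinic use there are at least 60 minutes of observation and an examination of the illumination site, and the oropharynx is examined on Days 1, 7 and 14. Section 6.2.3 has unsolicited events recorded from spontaneous report, open questions, observation, examination or other diagnostics. Section 6.2.10 has solicited and unsolicited events entered daily on the diary card.

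**The concern.** The solicited list is where the plan secures the same question for every subject every day. Two harms that the protocol itself describes for this device are not on it. One of them, eye damage, is potentially lasting, and Section 5.3.3 says that eye illumination is always to be avoided.

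The gap matters because of how the result will be read. Section 7.2 treats the absence of an event type as evidence that its rate is low. That holds only if events that happen are recorded. Events with no specific prompt are more likely to be missed, and these two can occur at home, where no one is watching. Reporting adds to the problem. Under Section 7.4.1 a solicited term has its own planned proportion and exact interval, so a zero would be shown as 0 out of 25. An unsolicited event that nobody reports would ordinarily have no row at all. Section 5.1.1 says the safety data will help to determine the regulatory pathway, so a silent zero could carry weight.

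**Working it through.** **1. Named risks (2.2.1) against the solicited list (6.2.2) and scheduled examination (6.2).**

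| Named risk | Condition in 2.2.1 | Solicited term | Scheduled look after screening |
|---|---|---|---|
| Mild local reactions | none | site pain, erythema, edema/induration | site and oropharynx, Days 1, 7, 14 |
| Erythema | use beyond directed time | yes | as above |
| Oral thermal injury | extreme overuse | not by name; pain, erythema, edema/induration and difficulty swallowing are plausible signs | as above |
| Gag reflex | improper insertion | none (nausea is a different event) | observation at clinic use only |
| Eye injury | direct illumination | none | none stated |

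**2. Share of use that is observed.** Twice daily for 14 days is 2 × 14 = 28 uses at most. Table 3 places device illumination in clinic on Days 1, 7 and 14. Assuming one use per visit, 3 are observed and 28 − 3 = 25 are at home (25/28 = 89%).

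**3. The plan's own detection figures.** With N = 25 and true rate p, P(at least one) = 1 − (1 − p)^25.
- p = 10%: 1 − 0.90^25 = 92.8%; the Section 7.2 table has 92.4%.
- p = 20%: 1 − 0.80^25 = 99.6%; the text has about 97%.
- p = 5%: 1 − 0.95^25 = 72.3%; the text has 90%.

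The last two do not reproduce. That is a separate matter, and the recalculated values are used below.

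**4. Allowing for incomplete capture.** If each affected subject is recorded with probability s, independently, then P(at least one recorded) = 1 − (1 − p·s)^25. The documents give neither p nor s for these harms, so both are assumed and shown as a range.

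| True rate p | s = 100% | s = 75% | s = 50% | s = 25% |
|---|---|---|---|---|
| 5% | 72.3% | 61.5% | 46.9% | 27.0% |
| 10% | 92.8% | 85.8% | 72.3% | 46.9% |
| 20% | 99.6% | 98.3% | 92.8% | 72.3% |

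For example, with p = 10% and s = 50%: 1 − (1 − 0.05)^25 = 72.3%.

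**5. What a zero would support.** With 0 of 25 recorded, the one-sided 95% upper bound on the true rate is (1 − 0.05^(1/25))/s. This is 11.3% at full capture, 15.1% at 75%, 22.6% at 50% and 45.2% at 25%. At 50% capture the bound exceeds the 20% that Section 7.2 uses as its example. The confidence attached to that example would be 92.8%, below the stated 97%.

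**The case against.** The strongest reply is that Section 6.2.2 does not promise to solicit every conceivable risk. It leaves the sponsor to choose the events for which consistent collection is wanted, and it equates them with reactogenicity. Section 2.2.1 ties eye damage and gagging to misuse and expects no significant acute risk when the device is used as directed. Section 5.2.1 describes a guard against over-insertion, and staff must make sure volunteers understand never to point the device at anyone's eyes. On this view the list is a legitimate choice. That stands to this extent: the documents show a gap in capture, not a contradiction of the definition.

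A reader might also infer that these harms would be recorded only if a subject volunteered them. The documents do not support that. Section 6.2 requires an interim history at every later visit, Section 6.2.3 admits open questions and observation, and the diary takes unsolicited events daily. Gagging in clinic can be seen during use, and the tolerability survey may ask about it. The survey items and the diary card are not shown, so this cannot be settled.

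A further tempting inference is that oral thermal injury is equally exposed. It is not. Four solicited terms are its plausible signs, and the tissue is examined at all three device-use visits. Nor are eye injury and gagging the only device risks named: erythema and local reactions are named too, and both are solicited.

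Finally, 5% or 10% may be high for misuse events, and prompting would not bring capture to 100%. Both points are fair, and they limit the arithmetic to an illustration. They leave the list comparison untouched: misuse is most likely in unsupervised home use, and no specific question about either harm is stated for that setting.

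**Conclusion.** The point holds for eye effects first and for gagging during home use second. Both are named in Section 2.2.1, neither is solicited in Section 6.2.2, and no scheduled eye assessment is stated after screening. At home they reach the record only by non-specific routes, so an observed zero would be weaker evidence than Section 7.2 assumes.

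The loss cannot be measured from the documents. At an assumed true rate of 10% and 50% capture, detection drops by 92.8 − 72.3 = 20.5 percentage points, and the upper bound after zero events doubles from 11.3% to 22.6%. These figures rest on assumed rates, assumed capture fractions and independence between subjects. The point does not extend to oral thermal injury, and it does not show that the plan has no means of recording eye or gag events. It is a cheap improvement to safety capture, not a flaw that invalidates the design.

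**What to change.** Add two terms to the solicited list in Section 6.2.2, to the diary card and to the Day 1, 7 and 14 prompts: eye discomfort or visual change, and gagging during use. Summarise them with the other solicited AEs under Section 7.4.1, so that a zero appears with its exact interval.

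Record any light shone into an eye as a separate yes/no item. It is a use error rather than a gradable event and does not fit the split in Section 7.4.1 between none and mild, moderate or severe. Present it as a listing. No new term is needed for oral thermal injury.

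The cost is three lines on a diary card that is already completed daily, with matching e-CRF fields. The downside is a slightly longer card and more mild events reported. Dose, schedule and clinical management are unaffected.
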